assessments	Waist circumference	11.5.1.2	X						X						
	Sagittal diameter	11.5.1.3	X						X						
	Bio-impedance	11.5.1.4	X						X						
Blood and	Liver function ²	11.6.5	X						X						
urine sampling (fasting)	HbA1c, glucose, insulin, triglycerides, total cholesterol, LDL, HDL, Hs-CRP, albumin	11.5.2	X						X						
	Exploratory: ApoA1, ApoB	11.7.1	X						X						
	Exploratory: orlistat and acarbose plasma levels ³	11.7.2							X						
Vital signs	Vital Signs	11.6.3	X						X						

CONFIDENTIAL 41 (92)

Clinical Study Protocol EP-002 Final version v3.0 12NOV2020

Category	Visit	Refer to			Visi	t 2					Visit 3	3 to 5		
	CSP Section	At the clinic				At home		At the clinic			At home			
	Assessment		Before breakfast	00:00	01.00	02:00	03:00	04:00	Before breakfast	00:00	01.00	02:00	03:00	04:00
Questionnaires	Meal pattern	11.5.4.1	(X) ⁴						(X) ⁴					
	GSRS	11.5.4.2	(X) ⁴						(X) ⁴					
	Satiety and craving	11.5.4.3	X		X	X	X	X	X		X	X	X	X
	Activity and sleep	11.5.4.4	(X) ⁴						(X) ⁴					
	Health and quality of life RAND-36	11.5.4.5	(X) ⁴						(X) ⁴					
IMP	Randomisation	9.9	X											
	Dispense IMP		(X) ⁵						(X) ⁵					
	IMP administration halfway into meal	10.5		X^6				X ⁶		X ⁷				X ⁷
	IMP compliance	10.7							(X) ⁴					
Food	Standardised breakfast			X						X				
Patient	Diary instruction	11.2	X											
instructions	Diet recommendations	9.6.1.2	(X) ⁴											
AEs and	Baseline symptoms	11.3.10	X											
medication	AEs	11.6.1				X					X			
	Prior and concomitant medication	11.3.5			X						X			

- 1. WOCBP only, urine test.
- 2. Liver enzymes: ALT, AST, ALP, GGT.
- 3. Orlistat and acarbose plasma levels: steady-state sample pre-dose at Visit 5, no sampling at Visit 3 or 4.
- 4. Does not have to be performed before breakfast. For further details on timing of questionnaires, refer to Table 11.5-2.

CONFIDENTIAL 42 (92)

Clinical Study Protocol EP-002 Final version v3.0 12NOV2020

- 5. IMP will be handed out at Visit 2, 3, and 4.
- 6. Visit 2: all patients will receive a placebo capsule during breakfast at the clinic. First randomised IMP dose in association with lunch at home.
- 7. Visit 3 and 4: IMP dose during breakfast (at clinic). Second and third IMP dose during subsequent meals at home. Visit 5: last dose at the clinic during breakfast, no other dose that day.

CONFIDENTIAL 43 (92)

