Eligible and consenting patients will arrive at the research clinic in the morning of the first dosing day (Day 1, Visit 2) after at least 8 hours overnight fasting. A re-check of eligibility including a brief physical examination, vital signs and assessment of body weight will be conducted.

The patients will be randomised to either of two doses of EMP16-02 or placebo:

- 1. EMP16-02 120 mg O/40 mg A
- 2. EMP16-02 150 mg O/50 mg A
- 3. Placebo (identical capsules)

Blood sampling (fasting), and anthropometric measurements will be performed. Patients will receive electronic diary instructions and will be asked to fill in a satiety and craving questionnaire before breakfast (at the clinic), and then once every hour for 4 hours until before lunch (at home). A standardised breakfast will be served at the clinic. Halfway through breakfast at Visit 2, all patients will receive a placebo capsule independent of the treatment arm to which the patients have been randomised, to provide the patients with the opportunity to train on self-administering the IMP under supervision of clinic staff. The patients will also receive instructions for filling in more questionnaires regarding health and quality of life, meal pattern, activity and sleep, and gastrointestinal symptoms (gastrointestinal rating scale [GSRS], as outlined in Section 11.5.4.

The patients will be instructed to take EMP16-02 or placebo halfway through each meal, together with approximately 100-200 mL water (or other drink) on all subsequent treatment days. Once IMP has been handed out, the patients are free to leave the clinic. The first randomised IMP dose will be taken during lunch (or the next meal) at home. See Table 8.1-4 for a detailed schedule of events for Visit 2.

Patients randomised to EMP16-02 will start with a run-in period of 6 weeks during which the dose is sequentially increased. From week 7, all patients will have reached their final intended dose and a 20-week treatment and observation period will start. The run-in phase will start at a dose of 60 mg O and 20 mg A TID, which will sequentially be increased with 30 mg O/10 mg A every two weeks until the target doses of 120 mg O/40 mg A TID (for the lower dose group) and 150 mg O/50 mg A TID (for the higher dose group) are reached. The dosing regimen is summarised in Table 8.1-1.

Table 8.1-1 Increasing dosing regimen

Target dose	Week 1 and 2	Week 3 and 4	Week 5 and 6	Week 7 to 26

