11.5.1.2 Waist circumference

Waist circumference will be measured in cm (one decimal) at visits specified in Table 8.1-3.

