11.5.3 Blood pressure

Systolic and diastolic blood pressure and pulse will be measured in supine position after 10 minutes of rest. Blood pressure is both an efficacy assessment and a safety assessment (Section 11.6.3) and should be registered in the vital signs form of the eCRF.

For timing of assessments refer to Table 8.1-3.

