17.1 General

Continuous data will be presented in terms of evaluable and missing observations, arithmetic mean, standard deviation (SD), median, minimum and maximum value.

Categorical data will be presented as counts and percentages. When applicable, summary data will be presented by treatment, and by assessment time. Individual patient data will be listed by patient number, treatment, and, where applicable, by assessment time.

All descriptive summaries and statistical analyses will be performed using SAS Version 9.4 or later (SAS Institute, Inc., Cary, NC).

Baseline will be defined as the visit with last data collection point prior to the first administration of IMP.

Outliers will be included in summary tables and listings and will not be handled separately in any analyses. No imputation of data will be performed neither for dropouts nor for missing data. An analysis of dropouts will be performed as detailed in Section 17.6.6.

All hypothesis testing will use a significance level of 5%.

Comparisons will be made pairwise and analysed at each visit if not stated otherwise.

CONFIDENTIAL 81 (92)

17.2 **Determination of sample size**

The hypothesis is to show that patients treated with EMP16-02 have a greater relative change (reduction) in body weight compared to placebo. The estimated treatment difference should be 5% with a standard deviation of 8%, a power of 80% and a significance level of 5% based on two-sided hypothesis testing. Using PASS V16.0 (method compare means), the number of evaluable patients needed per treatment arm is calculated to 41 patients. An evaluable patient is defined as a patient who has completed 26 weeks of treatment with IMP. Taking into account an estimated drop-out frequency of 20%, a total of 156 patients need to be randomised.

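### Blood pressure, waist and sagittal diameter are each read at two pre-dose visits, but baseline uses only the second; averaging both, with an own-baseline covariate, would recover some precision on these secondary endpoints

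*Protocol*

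**What the plan says.** Table 8.1-3 (Section 8.1) marks vital signs, waist circumference and sagittal diameter at Visit 1 (Day -28 to Day -1) and again at Visit 2 (Day 1). The narrative for Visit 2 confirms the repeat of vital signs: "A re-check of eligibility including a brief physical examination, vital signs and assessment of body weight will be conducted". The measurement sections add nothing on replicates. Section 11.5.3 has "Systolic and diastolic blood pressure and pulse will be measured in supine position after 10 minutes of rest", and Section 11.5.1.2 has "Waist circumference will be measured in cm (one decimal) at visits specified in Table 8.1-3".

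Section 17.1 fixes the baseline: "Baseline will be defined as the visit with last data collection point prior to the first administration of IMP". For these variables that is Visit 2, which the schedule also labels as baseline.

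Sections 17.6.2 and 17.6.4 analyse the absolute changes in waist, sagittal diameter and blood pressure by ANCOVA on treatment and baseline body weight. The relative change in blood pressure is analysed by ANOVA on treatment alone. The baseline of the variable being analysed is a covariate in none of these models.

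**The concern.** A change score carries the visit-to-visit noise of its baseline in full unless the model adjusts for that baseline. Here the model adjusts for body weight instead, and a second pre-dose reading that could halve the baseline noise is collected but not used in the change.

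These are tested secondary endpoints, compared pairwise in a trial sized for body weight alone at 41 evaluable patients per arm. Wider intervals than necessary on blood pressure and abdominal measures make a real effect harder to see, and the data to narrow them are already scheduled.

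**Working it through.** **The plan's own figure.** Section 17.2 takes a true difference of 5 points against an SD of 8, with a two-sided 5% test and 80% power, and concludes that "the number of evaluable patients needed per treatment arm is calculated to 41 patients". Normal approximation: n = 2(1.960 + 0.842)² × 8²/5² = 40.2, so 41. With 20% drop-out, 41/0.8 = 51.25, so 52 per arm and 156 in total. This reproduces and is not in dispute. It concerns body weight; the protocol states no SD or correlation for blood pressure, waist or sagittal diameter.

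**Notation.** B1 and B2 are the Visit 1 and Visit 2 readings and Y is a later reading, all with visit variance 1. Correlations are r12 (B1 with B2), r2 (B2 with Y) and r1 (B1 with Y). All values below are assumptions.

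**Change score, equal correlation ρ.**
- Var(Y − B2) = 2(1 − ρ)
- Var(Y − (B1+B2)/2) = 1 + (1+ρ)/2 − 2ρ = 1.5(1 − ρ)
- Ratio 0.75 for every ρ: 25% less variance, SE × √0.75 = 0.866.

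**Change score, general case.** The variances are 2 − 2·r2 (single) and 1.5 + r12/2 − r1 − r2 (mean).

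| r12 / r2 / r1 | single | mean | reduction |
|---|---|---|---|
| 0.65 / 0.55 / 0.50 | 0.900 | 0.775 | 14% |
| 0.70 / 0.55 / 0.45 | 0.900 | 0.850 | 6% |
| 0.95 / 0.85 / 0.82 | 0.300 | 0.305 | −2% (a loss) |

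Milder departures, with r1 = r2 between 0.5 and 0.8 and r12 higher by 0.05 to 0.10, give 12.5% to 22.5%.

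**Real differences in change between patients.** With true-change SD 5 cm and reading-error SD 2 cm for waist, the ratio is (25 + 1.5×4)/(25 + 2×4) = 31/33 = 0.94. With error SD 3 cm it is (25 + 1.5×9)/(25 + 2×9) = 38.5/43 = 0.90. The reduction is 6% to 10%.

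**Illustration for systolic pressure.** Assume visit SD 14 mmHg, ρ = 0.6, a 5 mmHg difference and 41 per arm (noncentral t). The SD of the change is 14√0.8 = 12.52 with one reading, giving 43.1% power. It is 14√0.6 = 10.84 with the mean, giving 54.1%. This is the favourable equal-correlation case.

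**Adding the own-baseline covariate.** Residual variance is 1 − r2² with B2 as covariate, and 1 − [(r1+r2)/2]²/[(1+r12)/2] with the mean. The last column compares the mean as covariate with the plan's change score.

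| r12 / r2 / r1 | plan's change score | covariate B2 | covariate mean | reduction against plan |
|---|---|---|---|---|
| 0.60 / 0.60 / 0.60 | 0.800 | 0.640 | 0.550 | 31% |
| 0.65 / 0.55 / 0.50 | 0.900 | 0.698 | 0.666 | 26% |
| 0.70 / 0.55 / 0.45 | 0.900 | 0.698 | 0.706 | 22% |
| 0.95 / 0.85 / 0.82 | 0.300 | 0.278 | 0.285 | 5% |

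The covariate improves on the plan in all four cases. Once it is in the model, averaging adds 14% in the first row and 5% in the second, and costs 1% and 3% in the last two. These figures ignore whatever baseline body weight already explains.

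**The case against.** The last pre-dose visit is a conventional baseline, and it is stated clearly and consistently. Nothing is invalid, and the trial is an exploratory Phase IIa study. That is fair, and it is why this is a question of efficiency and not of error.

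Averaging can also do harm. It raises the change-score variance when r2 − r1 exceeds (1 − r12)/2, as in the 0.95/0.85/0.82 case. That requires true drift over at most 28 days to outweigh reading noise, which is implausible for blood pressure and tape measures. Even there, adding the own-baseline covariate leaves the analysis ahead of the plan.

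Several stronger readings are tempting, and the documents do not support them:
- **A quarter of the variance is being lost.** That is a ceiling. It needs equal correlations and no real difference between patients in how much they change. Blood pressure at screening is also a selection reading (exclusion criterion 5), which makes equal variances and correlations less certain.
- **HbA1c, albumin and liver enzymes should be averaged too.** They appear in both the Visit 1 and Visit 2 panels, but the endpoints are defined as fasting, and note 5 to Table 8.1-3 says Visit 1 need not be fasting. The Visit 1 safety panel goes to a hospital laboratory (Section 11.6.5), and a common assay route for the HbA1c and albumin samples under Section 11.5.2 is not established.
- **Both readings precede randomisation.** Section 8.1 describes Visit 2 anthropometry after the randomisation step. What is documented is that the readings are pre-dose and the trial is double-blind, which is enough for the comparison with placebo to stay unbiased.
- **Visit 1 values enter no analysis.** Section 17.1 provides summaries by assessment time where applicable. The accurate statement is that Visit 1 is not used in the change from baseline.

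One practical objection stands. Blood pressure is also a safety variable summarised as change from baseline (Section 17.7.3), so it would have slightly different efficacy and safety baselines.

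**Conclusion.** The point holds for blood pressure, waist circumference and sagittal diameter. A scheduled pre-dose reading is left out of the change, and the models do not adjust for the variable's own baseline. Averaging alone would cut the variance of the change by at most 25%, and more likely by about 6 to 15%. The gain should be nearest the ceiling where day-to-day noise dominates, as is plausible for blood pressure, and smaller for waist and sagittal diameter, where true change varies between patients. Every SD and correlation behind these figures is assumed.

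A reader might infer that the comparison with placebo is biased or that the sample size is affected. Neither follows: the consequence is lost precision on secondary endpoints, and the primary endpoint and its 41 per arm are unaffected.

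**What to change.** In Section 17.1, for the efficacy analyses of systolic and diastolic blood pressure, waist circumference and sagittal diameter, define baseline as the mean of the Visit 1 and Visit 2 values, or Visit 2 alone if Visit 1 is missing. In Sections 17.6.2 and 17.6.4, add this own-baseline mean as a covariate in the ANCOVA models for these variables, stated openly as a change to the present treatment-plus-body-weight model.

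Keep Visit 2 as baseline for body weight, BMI, all laboratory markers (including HbA1c, albumin and liver enzymes) and all safety summaries. Make the change before unblinding.

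Cost: a few sentences and one derived variable per measure, with no new data. The Visit 1 reading may be up to 28 days older than Visit 2 and non-fasting. Within-arm changes will differ slightly from those under the last-visit convention, and the two blood pressure baselines need a clear label in the report.

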8.2 Rationale for study design

This study will provide a comprehensive analysis of the efficacy of EMP16-02 in reducing body weight and evaluates the effect on various anthropometric characteristics, satiety and craving, fasting metabolism markers, blood pressure and quality of life. In addition, this study will also provide insight in the safety and GI tolerability of EMP16-02. The design involves careful monitoring of the patient's well-being.

A placebo control will be used to establish the frequency and magnitude of changes in endpoints that may occur in the absence of active treatment.

Randomisation will be used to minimise bias in the assignment of patients to dose groups and to increase the likelihood that known and unknown patient attributes (*e.g.*, demographic and baseline characteristics) are balanced across the treatment groups.

Blinded treatment will be used to reduce potential bias during data collection and evaluation of endpoints.

8.3 **Selection of dose**

The following doses will be used in the study:

- 120 mg orlistat/40 mg acarbose
- 150 mg orlistat/50 mg acarbose

Because both orlistat and acarbose are associated with GI side effects and intolerability, and because the severity of these side effects is less when the dose is slowly increased, a 6-week run-in phase will be employed. In this phase, patients start at a low dose of 60 mg O/20 mg A, and sequentially increase the dose with 30 mg O/10 mg A every 2 weeks. From week 7, all patients have reached their target dose. For more information on dosing scheduling, see Section 8.1.

In the previous phase IIa study (EP-001), the primary comparison made was that between a dose of 90 mg O /30 mg A and a dose of conventional orlistat (Xenical, 120 mg). The rationale behind the lower dose of orlistat was that by optimising drug delivery, a lower dose of both orlistat and acarbose could still achieve a good efficacy. The highest orlistat dose used in the previous phase IIa study was 120 mg. No untoward effects on safety and tolerability were observed and there were no drop-outs in the treatment arm receiving 120 mg O / 40 mg A [28]. Since efficacy was highest in the group receiving 120 mg O / 40 mg A, it is now planned to test a dose that is slightly higher than conventional orlistat (conventional acarbose is given in dose strengths 50 mg or 100 mg TID). Dose levels of up to 240-400 mg orlistat have been studied for up to 6 months and did not result in any safety issues [31,32,33].

CONFIDENTIAL 44 (92)

9 STUDY POPULATION

Prospective approval of protocol deviations to eligibility criteria, also known as protocol waivers or exemptions, is not permitted.

9.1 **Recruitment**

The patients will be competitively recruited to both sites from CTC's database of healthy volunteers and patients, and from advertising in media (including social media).

9.2 Screening and enrolment log

Investigators must keep a record of all screened patients even if they were not subsequently included in the study. This information is necessary to verify that patients were selected without bias. The reason for screen failure should be stated for all patients screened but not included. The reason for withdrawal should be stated for all patients included but not completed.

A screening number will be allocated to each patient in connection to the informed consent process at the screening visit (Visit 1). The screening number is generated automatically in the eCRF. The screening number will allow identification of patients irrespective of their possible eligibility for the study. The screening number will have the following format: S0001 for the first patient screened, S0002 for the second, etc.

Patients included and randomised will be assigned a randomisation number from 101 to 256.

[figure not shown]
If a patient cannot receive the planned dose of IMP within 28 days after screening (*i.e.*, the time interval between signing informed consent until dose administration) the patient should be rescreened before proceeding in the study (see Section 9.7).

9.3 **Number of patients**

A total of 156 patients will be randomised in the main part of the study. Assuming a drop-out rate of 20%, a total of 52 patients will be randomised to each treatment arm to achieve at least 41 evaluable patients per arm. An evaluable patient is defined as a patient who has completed 26 weeks of treatment with IMP. An evaluable patient in the follow-up part is defined as a patient who has completed 26 weeks of treatment with IMP and the 6 months follow-up visit.

For replacements of patients who discontinue from the study, see Section 9.8.

CONFIDENTIAL 45 (92)

9.4 **Inclusion criteria**

For inclusion in the study, patients must fulfil the following criteria:

- 1. Willing and able to give written informed consent for participation in the study.
- 2. Aged \geq 18 and \leq 75 years.
- 3. Maximum weight of 150 kg and BMI \geq 30 or \geq 28 kg/m² in the presence of other risk factors based on patient interview, *e.g.*, hypertension (either or not treated with antihypertensive agents), glucose dysregulation such as impaired glucose tolerance (defined as elevated fasting glucose or HbA1c as judged by the Investigator) and T2DM that is treated with life style changes (no medication allowed), and/or dyslipidaemia (either or not treated with antihyperlipidemic agents). If indicated, plasma/serum total cholesterol, LDL, HDL, and triglycerides can be measured to verify eligibility as judged by the Investigator.
- 4. Acceptable medical history, physical findings, vital signs, ECG and laboratory values at the time of screening, as judged by the Investigator.
- 5. Adequate renal and hepatic function as judged by the Investigator in accordance with the expected disease profile
- 6. Weight stable (<5% reported change during the three months preceding screening), based on patient interview and weight assessments at screening (Visit 1) and randomisation (Visit 2).
- 7. Willing to eat three meals per day, and willing to eat breakfast during the visits to the clinic.
- 8. Males and females may be included in the study. WOCBP must agree to use a highly effective method of contraception with a failure rate of < 1% to prevent pregnancy (combined [oestrogen and progestogen containing] hormonal contraception associated with inhibition of ovulation [oral, intravaginal, transdermal], progestogen-only hormonal contraception associated with inhibition of ovulation [oral, injectable, implantable], intrauterine device [IUD]or intrauterine hormone-releasing system [IUS]) OR practice abstinence from heterosexual intercourse (only allowed when this is the preferred and usual lifestyle of the patient) from at least 4 weeks prior to first dose to 4 weeks after last dose.

Women of non-childbearing potential are defined as pre-menopausal females who are sterilised (tubal ligation or permanent bilateral occlusion of fallopian tubes); or post-menopausal defined as 12 months of amenorrhea (in questionable cases a blood sample with simultaneous detection of follicle stimulating hormone [FSH] 25-140 IE/L).

CONFIDENTIAL 46 (92)

9.5 Exclusion criteria

Patients must not enter the study if any of the following exclusion criteria are fulfilled:

- 1. T2DM treated with medication.
- 2. History of any clinically significant disease or disorder which, in the opinion of the Investigator, may either put the patient at risk because of participation in the study, or influence the results or the patient's ability to participate in the study.
- 3. Any clinically significant illness, medical/surgical procedure or trauma within 4 weeks prior to the first administration of IMP, at the discretion of the Investigator.
- 4. Any planned major surgery within the duration of the study.
- 5. Untreated high blood pressure (systolic blood pressure [SBP] > 160 mmHg and diastolic blood pressure [DBP] >100 mmHg at screening).
- 6. Use of any of the prohibited medication listed in Table 9.6-1 within 2 weeks prior to the first administration of IMP. Recently started use of anti-depressants (*e.g.*, selective serotonin re-uptake inhibitors [SSRI]) within 2 weeks prior to the first IMP administration or planned start of anti-depressant treatment during the study period is not allowed, yet patients that are on stable treatment with anti-depressants for at least two months can be included.
- 7. Known hypersensitivity to any of the test substances. History of hypersensitivity to drugs with a similar chemical structure or class to orlistat and acarbose.
- 8. Gastrointestinal problems/diseases, *e.g.*, inflammatory bowel diseases and Irritable Bowel Syndrome (IBS). Untreated gastroesophageal reflux disease (GERD) or GERD that is treated occasionally is allowed as judged by the Investigator.
- 9. Cholestasis.
- 10. Previous gastrointestinal surgery that might influence gastrointestinal function significantly, previous bariatric surgery, and previous gallbladder surgery as judged by the investigator.
- 11. Known vitamin B12 deficiency or other signs of achlorhydria.
- 12. Chronical malabsorption syndrome.
- 13. Clinically significant abnormal laboratory values at screening as judged by the investigator.
- 14. History of severe allergic, cardiac or hepatic disease. History of significant cardiovascular disease such as myocardial infarction, congestive heart failure, stroke, serious cardiac arrhythmias. History of angina within 6 months prior to screening.
- 15. A personal or family history of Medullary Thyroid Carcinoma (MTC).
- 16. A personal or family history of Multiple Endocrine Neoplasia syndrome type 2 (MEN 2).
- 17. Current or history of alcohol abuse and/or use of anabolic steroids or drugs of abuse, as judged by the Investigator.

CONFIDENTIAL 47 (92)

- 18. Positive screen for drugs of abuse at screening or admission to the clinic or positive screen for alcohol at screening or admission to the clinic prior to administration of the IMP.
- 19. Any positive result on screening for serum hepatitis B surface antigen, hepatitis C antibody and HIV.
- 20. Plasma donation within one month of screening or any blood donation (or corresponding blood loss) during the three months prior to screening.
- 21. Administration of another new chemical entity (defined as a compound which has not been approved for marketing) or participation in any other clinical study that included drug treatment within three months of the first administration of IMP in this study. Patients consented and screened but not dosed in previous studies are not excluded.
- 22. Investigator considers the patient unlikely to comply with study procedures, restrictions and requirements.
- 23. Malignancy within the past 5 years with the exception of in situ removal of basal cell carcinoma.
- 24. Prolonged QTcF (>450 ms for males, >470 for females), cardiac arrhythmias or any clinically significant abnormalities in the resting ECG at the time of screening, as judged by the Investigator.
- 25. Patients with swallowing disorders, which may affect the patient's capability to swallow the IMP.

9.6 **Restrictions during the study**

The patients must be willing to comply to the restrictions outlined in Section 9.6.1 during the entire main study duration *i.e.*, from screening to the safety follow-up visit (Visit 6) if not otherwise specified.

